APPENDIX C MAXIMUM PLUS MANIFEST REFRACTION TECHNIQUE WITH CYLINDER REFINEMENT

Manifest refraction testing will be performed using a self-illuminating light box and 100% contrast ETDRS charts designed for 4.0 meters with the room lighting set to that required for photopic distance visual acuity testing (85 cd/m²). NOTE: Objective refraction by either retinoscopy or autorefraction can be used as a starting point for the Manifest Refraction. Always ensure that the endpoint of refraction is maximum plus (or minimum minus) power that yields maximum visual acuity.

- 1) Occlude the fellow eye.
- 2) SPHERE: Starting with the objective refraction, refine the sphere to yield best visual acuity. **Important:** Add plus power (or reduce minus) until subject demonstrates at least a 1-line loss from best visual acuity (fogging). Then step down to the most plus (or least minus) sphere power until visual acuity and clarity show no improvement.
- 3) CYLINDER AXIS: Refine cylinder with a cross-cylinder and the objective cylinder refraction as the starting point. Refine axis first and power second, since the correct axis can be found with an incorrect power, but the correct power cannot be found with an incorrect axis.
 - a. Direct the subject's attention to 1 line above (larger letters) the best visual acuity. With the trial cylinder (axis and power) in the phoropter, introduce cross-cylinder for axis refinement. When asking the subject which cross-cylinder axis position is better, "one or two?", remind the subject to look at different letters on the line and report preference based on the overall clarity of the letters.
 - b. Refine the axis based on the subject's responses, using small steps (less than five degrees), until the subject reports no difference in the two choices.
 - c. Cylinder axis may be further confirmed by bracketing: Slowly rotate the trial cylinder in one direction until the subject reports blurring and note the axis. Rotate the trial cylinder in the opposite direction past the presumed axis until the subject reports blurring, again noting the axis. The average of the two noted axes can be taken as the final astigmatism axis.
- 4) CYLINDER POWER: Set the cross cylinder to refine cylinder power and present choices to the subject, reminding the subject to look at different letters on the line and report preference based on overall clarity of the letters. Reduce or increase trial cylinder power accordingly.
 - a. Maintain the spherical equivalent throughout cylinder power refinement by adjusting the sphere once for every two clicks of cylinder power change.
- 5) SPHERE CHECK: Introduce plus sphere in 0.25 D increments until the subject reports and demonstrates a reduction in visual acuity. Then reduce sphere power in 0.25 D steps until visual acuity and clarity show no improvement.

APPENDIX D REFRACTION ADJUSTMENTS

Postoperative study manifest refractions are to be performed using the 100% ETDRS charts at a distance of 4.0 meters. Because 4.0 meters is not optical infinity, refraction adjustments are necessary to ensure proper vision testing taking into account test distance and refraction distance. The adjustment required (in diopters) is 1/test distance (in meters). To adjust a 4.0-meter refraction to optical infinity, -0.25 D is to be added to the sphere of the refraction to obtain a true distance (infinity) correction. On the other hand, to adjust optical infinity to a 4.0-meter test distance, +0.25 D is to be given. In the case where the refraction distance (4.0 meters) and the vision test distance (4.0 meters) are the same, no adjustment is necessary. The following table lists the refraction adjustments required for the various vision tests in this study:

[figure not shown]
Refraction Adjustments for Vision Testing

Vision Test	Test Distance	Correction/Adjustment
Uncorrected distance visual acuity (UCDVA)	4.0 m	+0.25 D adjustment only
Best corrected distance visual acuity (BCDVA)	4.0 m	No adjustment; ETDRS Rx only
Best corrected distance defocus curve testing	4.0 m	No adjustment; ETDRS Rx only
Uncorrected intermediate visual acuity (UCIVA)	66 cm	No adjustment
Distance corrected intermediate visual acuity (DCIVA), 100% and 10% contrast	66 cm	-0.25 D added to ETDRS sphere Rx
Best corrected intermediate visual acuity (BCIVA, with add), 10% contrast	66 cm	-0.25 D added to ETDRS sphere Rx
Uncorrected near visual acuity (UCNVA)	40 cm	No adjustment
Distance corrected near visual acuity (DCNVA)	40 cm	-0.25 D added to ETDRS sphere Rx
Best corrected distance contrast sensitivity	2.5 m	+0.12 D added to ETDRS sphere Rx

APPENDIX E INSTRUCTIONS FOR USING THE M&S SYSTEM

Distance and intermediate visual acuity, low-contrast intermediate visual acuity, defocus, manifest cylinder defocus and contrast sensitivity testing will be performed using the M&S Technologies CTS-1000 Smart System[®] computerized vision testing system (M&S System). This system provides descending LogMAR charts with proportionally spaced SLOAN letters at 100% contrast for high contrast visual acuity and defocus testing, 10% contrast for low-contrast intermediate visual acuity and appropriate contrast levels for contrast sensitivity testing. Each presentation is randomized and is consistent and repeatable. The system is calibrated for both distance to subject and pixels/inch so that optotypes precisely follow ANSI Z80.21-2010 and ISO 8596:2000 in regard to size, spacing between optotypes and spacing between lines.

Figure 4: Example of LogMAR 4.0 meter chart screen

The M&S System background luminance is automatically set to 85 cd/m² (range of 80-110 cd/m² is acceptable) for photopic testing, and 3 ± 0.5 cd/m² for mesopic testing. Room lighting is to be set to a level lower than the illumination from the laptop screen. Ambient lighting should be dim to dark (less than 50 lux) to maximize pupil size. No surface (including reflective surfaces) within the subject’s field of vision should be brighter than the chart background in luminance. The room lighting and screen luminance will be verified each time the computer is turned on using the AMO-provided, auto-adjusting, monitor-calibration system to ensure light levels are appropriate.

The M&S System will be set up to perform required visual tests in a specific order, with prompts on the screen to allow the technician to set up the subject for monocular or binocular testing, refraction adjustments as needed and uncorrected or best corrected testing. Letters on all charts will appear randomly, with the technician controlling movement through charts based on subject responses.

As a subject completes a visual acuity line, the technician will select the total number of letters correctly read for that line on the handheld controller, press “Enter” and then

confirm the number of letters correct at the next prompt. The M&S System will then advance to the next line of testing and the process will repeat. The system will end the test when the subject no longer has any correct responses. The number of letters correctly read will be displayed on the laptop screen, along with the LogMAR value and Snellen acuity. Record the total number of letters read. A similar process will be done for contrast sensitivity grating responses. Once a test is completed, follow the prompts on the computer screen to start the next test.

Test results are stored in the M&S computer and a hard copy will be printed and validated as a back-up.

APPENDIX F INSTRUCTIONS FOR DISTANCE VISUAL ACUITY TESTING

For distance visual acuities, the M&S System laptop should be placed at a test distance of 4.0 meters from the subject for testing distance visual acuities. A laptop setting may be used to reverse charts for rooms that require “folding” via a mirror to reach a distance of 4.0 meters. Whether standard or “folded”, measure and record the test distance accurately. If the room set-up does not allow the computer to be placed at precisely 4.0 meters, the M&S System can be adjusted to account for the actual test distance used.

The M&S System will be set up to perform the required distance visual acuity tests in a specific order, with prompts on the screen to allow the technician to set up the subject for monocular or binocular testing, refraction adjustment as needed and uncorrected or best corrected testing.

Subjects should be reminded prior to testing that squinting is not allowed. The technician is to observe the subject to ensure the subject is not squinting during visual acuity testing. If squinting is observed, the subject is to be reminded by the testing technician not to squint.

Distance visual acuity measurements are to be performed per the visit schedule in **Appendix A**. Monocular testing is required on the first eye implanted only; to test subjects monocularly, occlude the second eye in the phoropter or with an occluder if trial lenses are used.

Visual acuity measurements are based on the total number of correctly read letters. Subjects should be persuaded to read the smallest letters possible even if they have to guess. Follow the testing process listed in **Appendix E**. At the end of the test, the number of letters correctly read will be displayed on the laptop screen, along with the LogMAR value and Snellen acuity. Record the total number of letters read in the EDC system.

APPENDIX G INSTRUCTIONS FOR INTERMEDIATE VISUAL ACUITY TESTING

Intermediate visual acuity will be measured using the M&S System at a test distance of 66 cm. Subjects should be reminded prior to testing that squinting is not allowed. Trial frames should be used for visual acuity testing with careful observation by the testing technician to ensure the subject is not squinting. If squinting is observed, the subject is to be reminded by the testing technician not to squint.

The M&S System will be set up to perform the required intermediate visual acuity tests in a specific order, with prompts on the screen to allow the technician to set up the subject for monocular or binocular testing, refraction adjustment as needed, and uncorrected or best corrected testing.

Subjects should be reminded prior to testing that squinting is not allowed. Trial frames should be used for visual acuity testing with careful observation by the testing technician to ensure the subject is not squinting. If squinting is observed, the subject is to be reminded by the testing technician not to squint.

Intermediate visual acuity measurements are to be performed per the visit schedule in **Appendix A**. Both 100% contrast and 10% contrast intermediate acuity tests will be done on the M&S System. Monocular testing is required on the first eye implanted only; to test subjects monocularly, occlude the second eye in the phoropter or with an occluder if trial lenses are used.

Visual acuity measurements are based on the total number of correctly read letters. Subjects should be persuaded to read the smallest letters possible even if they have to guess. Follow the testing process listed in **Appendix E**. At the end of the test, the number of letters correctly read will be displayed on the laptop screen, along with the LogMAR value and Snellen acuity. Record the total number of letters read in the EDC system.

BEST CORRECTED INTERMEDIATE VISUAL ACUITY TESTING WITH ADD (BCIVA):
First eye monocular best corrected intermediate visual acuity (10% contrast) with minimum add will be performed to determine the minimum amount of add necessary to achieve an intermediate visual acuity similar to the best corrected distance visual acuity. BCIVA is to be tested at 66 cm under photopic conditions using the M&S System at 6 months. With distance correction in place, slowly build the amount of add necessary for the subject to achieve their best monocular low-contrast intermediate visual acuity in the primary eye. In order to ensure the appropriate amount of add, at least one of the criteria given below must be achieved:

BCIVA similar to the subject's BCDVA. Document the amount of add necessary to achieve a BCIVA that matches the subject's BCDVA in the first eye. For example, if the subject's BCDVA is 20/20, the minimum ADD power will be the amount of add necessary to achieve a BCIVA of 20/20 at 66 cm. When the subject reaches a BCIVA that matches the BCDVA, record the minimum add power and BCIVA (# of letters correct).

Increasing ADD power does not lead to improvement in near visual acuity.

When an additional +0.50 add (in two +0.25 D increments) does not increase the subject's visual acuity by 3 or more letters, stop the test and record the minimum add power and BCIVA (# of letters correct). For example, the subject shows progressive improvement in intermediate visual acuity and achieves 20/25 with +0.75 add over the distance correction. Increasing the add further by +0.50 (in two +0.25 D increments) only allows the subject to get 20/25+2 with a total of +1.25 add power. Stop the testing and record a minimum add of +0.75 with 75 letters correct.

APPENDIX H INSTRUCTIONS FOR NEAR VISUAL ACUITY TESTING

Near visual acuity will be measured using a using Good-Lite 100% ETDRS near charts designed for 40 cm and the Good-Lite self-illuminated and self-calibrated illumination box. The Good-Lite illumination box is self-illuminated and self-calibrates to a light level of approximately 85 cd/m² (range of 80–110 cd/m² is acceptable). Room lighting is to be set at a level lower than the illumination from the light box, per manufacturer instructions. Ambient luminance should be from dim to dark to maximize pupil size. No surface (including reflective surfaces) within the subject's field of vision should exceed the chart background in luminance.

The light box should be placed at a test distance of 40 cm from the subject for testing near visual acuities. Subjects should be reminded prior to testing that squinting is not allowed. Trial frames should be used for visual acuity testing with careful observation by the testing technician to ensure the subject is not squinting. If squinting is observed, the subject is to be reminded by the testing technician not to squint.

To avoid chart memorization, charts will be changed between every visual acuity measurement. Monocular testing will be required on the first eye implanted only, with the second eye occluded. Uncorrected and distance corrected monocular testing on the first eye will be completed before binocular testing is done.

Near visual acuity testing is to be performed per **Appendix A**. Visual acuity measurements are based on the total number of correctly read letters. Subjects should be persuaded to read the smallest letters possible even if they have to guess. Record the total number of letters read correctly for each near test on the case report form. Near score grids are to be used and must be retained as source documentation. A reference chart for the conversion of the number of correctly-read ETDRS letters to a Snellen line equivalent is provided later in this section.

PROCEDURE: Begin with monocular uncorrected near visual acuity testing for the first eye implanted, and instruct subjects to start from the top, reading each line from left to right until they cannot read any additional letters. Alternate the near chart per the score sheet and repeat the testing with distance correction in place. For binocular testing, change the near charts per the score sheet and test uncorrected and distance corrected binocular acuities. Record the total number of letters read for each test condition in the EDC system.

Conversion Reference Chart for GOOD-LITE Near (40 cm) Chart (ETDRS)

Standard Snellen Line Equivalent	Number of ETDRS Letters Read at 40 cm	Standard Snellen Line Equivalent	Number of ETDRS Letters Read at 40 cm
20/10	85	20/50	49
	84		48
	83	20/60	47
20/13	82		46
	81		45
	80		44
	79	43	
	78	20/80	42
20/16	77		41
	76		40
	75		39
	74	38	
	73	20/100	37
20/20	72		36
	71		35
	70		34
	69	33	
	68	20/126	32
20/25	67		31
	66		30
	65		29
	64		28
	63	20/160	27
20/32	62		26
	61		25
	60		24
	59	23	
	58	20/200	22
20/40	57		21
	56		20
	55		19
	54		18
	53	>20/200	17
20/50	52		16
	51		15
	50		

APPENDIX I INSTRUCTIONS FOR DEPTH OF FOCUS TESTING

All depth of focus testing is to be performed under photopic conditions using the M&S System at a test distance of 4.0 meters. Subjects should be reminded prior to testing that squinting is not allowed. During defocus curve testing, trial frames will be used to allow observation by the testing technician to ensure the subject is not squinting. If squinting is observed, the subject is to be reminded by the testing technician not to squint.

This test is to be done monocularly at the 1-month visit for all subjects and binocularly at the 6-month visit for all subjects. Only the first eye implanted will be tested at the 1-month visit.

Monocular Depth of Focus Testing (1-month visit): With the subject's distance correction in place for the first eye and the second eye occluded, defocus the image by +2.00 D over the manifest distance correction in the first eye. Start the test by instructing the subject to read as many letters as possible on the M&S system, even if they have to guess. The technician will control movement through charts based on subject responses and the system will end the testing when a threshold is reached. The number of letters correctly read and the LogMAR score will be displayed on the laptop screen; record the total number of letters correct in EDC. Continue to change the defocus in -0.50 D increments, repeating the test and recording the total number of letters correct at each level of defocus. Continue to change the defocus to -4.00 D over the subject's distance correction.

Binocular Depth of Focus Testing (6-month visit): Begin binocular testing by defocusing the image by +2.00 D over the manifest distance correction in both eyes. Start the test by instructing the subject to read as many letters as they can on the M&S system, even if they have to guess. The technician will control movement through charts based on subject responses and the system will end the testing when a threshold is reached. The number of letters correctly read and the LogMAR score will be displayed on the laptop screen; record the total number of letters correct in EDC. Continue to change the defocus in -0.50 D increments in both eyes, repeating the test and recording the total number of letters correct at each level of defocus. Continue to change the defocus to -4.00 D over the subject's distance correction.

APPENDIX J INSTRUCTIONS FOR MANIFEST CYLINDER DEFOCUS TESTING

All manifest cylinder defocus testing is to be performed binocularly on all subjects at the 1-month study visit under photopic conditions using the M&S System at a test distance of 4.0 meters. Subjects should be reminded prior to testing that squinting is not allowed. During manifest cylinder defocus testing, trial frames will be used to allow observation by the testing technician to ensure the subject is not squinting. If squinting is observed, the subject is to be reminded by the testing technician not to squint.

Begin binocular testing by placing the manifest refraction (sphere and cylinder) in place for both eyes. Add cylindrical power -0.50 D over the distance correction in both eyes, maintaining the same axis as the manifest refraction (or place at 90 axis for subjects with no refractive cylinder). Start the test by instructing the subject to read as many letters as they can on the M&S system, even if they have to guess. The technician will control movement through charts based on subject responses and the system will end the testing when a threshold is reached. The number of letters correctly read and the LogMAR score will be displayed on the laptop screen; record the total number of letters correct in EDC. Continue to change the amount of in -0.50 D increments in both eyes, repeating the test and recording the total number of letters correct at each level of defocus. Continue to change the defocus to -3.00 D over the subject's distance correction and record the number of letters correct for each cylinder lens.

APPENDIX K INSTRUCTIONS FOR PUPIL SIZE MEASUREMENTS

Pupil size under photopic and photopic with glare conditions should be measured by a Colvard pupillometer (Oasis Medical), a NeurOptics pupillometer (NeurOptics, Inc.) or a pupil card. A Colvard or NeurOptics pupillometer should be used for measuring pupil size under mesopic and mesopic with glare conditions. For consistency, the same method should be used throughout the study. Pupil size should be recorded to the nearest one-half millimeter (one-tenth millimeter for NeurOptics).

PHOTOPIC PUPIL SIZE:

Photopic pupil size for each eye should be measured under the same lighting conditions as the photopic distance visual acuity testing. To measure photopic pupil size, have the subject look at a spot in the distance (without glasses) and allow one eye to be exposed to the ambient room lighting while measuring the other pupil of the other eye. Repeat the measurement on the second eye, and record the photopic pupil size for both eyes.

PHOTOPIC WITH GLARE PUPIL SIZE:

Photopic with glare pupil size for each eye should be measured under the same lighting conditions as the photopic with glare contrast sensitivity testing. To measure photopic with glare pupil size, have the subject (without glasses) look at a spot on the photopic with glare contrast sensitivity chart and allow one eye to continuously be exposed to the lighting condition while measuring the pupil of the other eye. Repeat the measurement on the second eye, and record the photopic with glare pupil size for both eyes.

MESOPIC PUPIL SIZE:

Mesopic pupil size for each eye should be measured under mesopic conditions. Room lights should be off and the 1.5 ND filter placed in front of the M&S System to reduce the lighting to 3 cd/m². After 10 minutes of dark light adaptation, have the subject (without glasses) look at a spot on the mesopic contrast sensitivity chart and allow one eye to continuously be exposed to the lighting condition while measuring the pupil of the other eye. Repeat the measurement on the second eye, and record the mesopic pupil size for both eyes.

MESOPIC WITH GLARE PUPIL SIZE:

Mesopic with glare pupil size for each eye should be measured under mesopic with glare contrast sensitivity conditions. Room lights should be off and the 1.5 ND filter placed in front of the M&S System to reduce the lighting to 3 cd/m², with the glare lights on. Have the subject (without glasses) look at a spot on the mesopic with glare contrast sensitivity chart and allow one eye to continuously be exposed to the lighting condition while measuring the pupil of the other eye. Repeat the measurement on the second eye, and record the mesopic with glare pupil size for both eyes.

APPENDIX L INSTRUCTIONS FOR CONTRAST SENSITIVITY TESTING

Contrast sensitivity testing will be measured using the M&S system for sine-wave gratings (1.5, 3, 6, 12 and/or 18 cycles per degree). Testing will be done under mesopic, mesopic with glare and photopic with glare lighting conditions. **The test distance for the M&S system is 8 feet (2.5 meters).** Mesopic testing without glare will be performed before contrast sensitivity with glare testing.

This test is to be done monocularly at the 1-month and binocularly at the 6-month visit for all subjects. Only the first eye implanted will be tested at the 1-month visit. All subjects will be tested with best corrected manifest refraction in place, and a refraction adjustment of +0.12 D over manifest refraction in place. Subjects should be shown the contrast sensitivity target samples before dark adaptation for mesopic testing is started.

Contrast sensitivity measurements are based on subject identification of the orientation of a low contrast grating (vertical, horizontal, tilted left or tilted right). For each grating presented, the subject will have to identify or guess the orientation of the grating. After an automated protocol, contrast sensitivity values will be displayed on the laptop screen for 1.5, 3, 6, 12 and/or 18 cpd.

Monocular Testing (1-month visit): The test will begin with the mesopic without glare lighting condition. Dim to dark room lighting will be used along with a 1.5 ND filter in front of the M&S system laptop computer screen. Dark adapt the subject for 10 minutes and measure mesopic pupil size per **Appendix K** prior to beginning the test. Place the subject's distance correction with the +0.12 D refraction adjustment in place for the first eye implanted and occlude the second eye implanted. Place a 1.5 ND filter in front of the subject's first eye implanted and an occluder in front of the second eye implanted in the trial frames before removing the 1.5 ND filter from the front of the M&S System. Begin testing and instruct the subject to report the orientation of the contrast grating out loud as they view the grating, documenting the subject responses on the M&S tablet. Encourage the subject to continue through all gratings, even if they have to guess. The M&S System will advance to the next set of gratings based on the technician input of the subject's responses. Record the contrast sensitivity percentages displayed on the laptop computer for all the spatial frequencies in EDC.

Proceed to mesopic with glare and photopic with glare testing, measuring the pupil size per **Appendix K** prior to beginning each test.

Binocular Testing (6-month visit): The test will begin with the mesopic without glare lighting condition. Dim to dark room lighting will be used along with a 1.5 ND filter in front of the M&S system laptop computer screen. Dark adapt the subject for 10 minutes and measure mesopic pupil size per **Appendix K** prior to beginning the test. Place the

subject's distance correction with the +0.12 D refraction adjustment in place for both eyes. Place a 1.5 ND filter in front of the subject's first eye implanted and an occluder in front of the second eye implanted in the trial frames before removing the 1.5 ND filter from the front of the M&S System. Begin testing and instruct the subjects to report the orientation of the contrast grating out loud as they view the grating, documenting the subject responses on the M&S tablet. Encourage the subject to continue through all gratings, even if they have to guess. The M&S System will advance to the next set of gratings based on the technician input of the subject's responses. Record the contrast sensitivity percentages displayed on the laptop computer for all the spatial frequencies in EDC.

Proceed to mesopic with glare and photopic with glare testing, measuring the pupil size per **Appendix K** prior to beginning each test.

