APPENDIX A SUMMARY OF PROCEDURES REQUIRED AT EACH VISIT

Shaded lines indicate masked testing

Examination	Preop Both eyes	Op 1 st eye and 2 nd eye	1 day 1 st eye and 2 nd eye	1 week 1 st eye and 2 nd eye	1 month Both eyes	6 months Both eyes
Informed consent, ocular history, inclusion/exclusion criteria ^a , potential visual acuity, targeted refraction, IOL power calculations, biometry and randomization if required	X					
Lens power/serial number (masked)/operative procedures		X				
Manifest refraction (Snellen preop; ETDRS postop)	X			X	X	X
UCDVA - photopic, monocular (Snellen preop; ETDRS postop) ^c	X			X	X	X
UCDVA - photopic, binocular (ETDRS)					X	X
BCDVA - photopic, monocular (Snellen preop; ETDRS postop) ^c	X			X	X	X
BCDVA - photopic, binocular (ETDRS)					X	X
UCIVA and DCIVA - photopic, monocular at 66 cm (ETDRS) ^c					X	X
UCIVA and DCIVA - photopic, binocular at 66 cm (ETDRS)					X	X
UCNVA, DCNVA, BCNVA - photopic, monocular at 40 cm (ETDRS) ^c					X	X
UCNVA and DCNVA - photopic, binocular at 40 cm (ETDRS)					X	X
DCIVA and BCIVA, monocular, low contrast acuity (10%) ^c						X
Defocus testing, monocular ^c (M) and binocular (B)					M	B
Tolerance to cylinder testing, binocular					X	
Contrast Sensitivity testing, monocular ^c (M) and binocular (B)					M	B
Pupil size (photopic and under contrast sensitivity conditions)					X	X
Keratometry	X ^b				X	
Intraocular pressure	X		X	X	X	X
Biomicroscopic slit-lamp exam ^b	X		X	X	X	X
Dilated fundus exam with fundus visualization	X					X
Adverse events		X	X	X	X	X
Ocular medications	X	X	X	X	X	X
Ocular/visual symptoms (non-directed)	X		X	X	X	X
Subject questionnaires	X				X	X

^a With corneal stability check for contact lens wearers

^b Includes determination of medical and lens findings/complications

^c Monocular testing required for first-eye only

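### Appendix L's set-up for the 6-month binocular contrast sensitivity test occludes the second eye, so as written the mesopic test without glare is done with one eye

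*Protocol*

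**What the plan says.** Appendix L opens with the intended mode: "This test is to be done monocularly at the 1-month and binocularly at the 6-month visit for all subjects". Three other places agree:

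- Protocol Appendix A, in the row beginning "Contrast Sensitivity testing, monocular", shows M at 1 month and B at 6 months.
- SAP 7.4 gives the same schedule.
- SAP Appendix I lists a 6-month table for binocular contrast sensitivity.

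In the 6-month paragraph of Appendix L, the first step is consistent with this. It puts the "distance correction with the +0.12 D refraction adjustment in place for both eyes". The next sentence reads "Place a 1.5 ND filter in front of the subject's first eye implanted and an occluder in front of the second eye implanted", and testing then begins. For the remaining two lighting conditions the paragraph says only "Proceed to mesopic with glare and photopic with glare testing, measuring the pupil size per" Appendix K.

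The Synopsis and SAP 1 name binocular best corrected contrast sensitivity as an additional safety endpoint. Protocol 6 sets 6 months as the key timeframe for safety.

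**The concern.** An eye behind an occluder contributes nothing to the score, so a test set up this way is monocular whatever its heading says. A technician who follows the written steps would record first-eye results at the visit meant to supply the binocular safety data. One who follows the heading would test both eyes. With up to 14 sites, the table labelled binocular could hold first-eye values or a mixture.

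The mistake would be hard to repair. Appendix A schedules the binocular test once, at the last study visit. Appendix L asks for the contrast percentages to be entered, and no section asks for the eye set-up to be recorded. SAP 7.4 then stratifies the binocular scores by the average of the two pupil sizes, which does not fit a one-eye measurement.

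**Working it through.** **The plan's own figure for this endpoint.** Protocol 20.6 and SAP 8 state 80% power for contrast sensitivity with margin 0.15 log units, SD 0.34, one-sided alpha 0.05 and 65 per group.

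- Normal approximation: power = Φ(0.15 / (0.34 × √(2/65)) − 1.645) = Φ(2.515 − 1.645) = Φ(0.870) = 80.8%.
- Noncentral t with 128 degrees of freedom: 80.4%.
- Required size: 2 × 0.34² × (1.645 + 0.842)² / 0.15² = 63.5, so 64 per group against 65 planned.

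The figure reproduces. The concern does not depend on it.

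**The two Appendix L paragraphs side by side.**

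| Step | 1 month, monocular | 6 months, binocular |
|---|---|---|
| Distance correction with +0.12 D | First eye; second eye occluded | Both eyes |
| Trial-frame set-up | 1.5 ND filter on first eye, occluder on second | Identical: 1.5 ND filter on first eye, occluder on second |
| Next step | Testing begins | Testing begins |
| Glare conditions | Proceed, with pupil measurement | Proceed, with pupil measurement |

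The correction step was adapted for two eyes and the filter and occluder step was not. Nothing between that step and the start of testing removes the occluder or puts a filter on the second eye.

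**Does another section supply a binocular set-up?** No.

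- Appendix K places the filter in front of the M&S System for mesopic pupil measurement. It does not describe the trial frame during testing.
- Appendix I, for binocular depth of focus at the same visit, is written for two eyes with no occluder: "Begin binocular testing by defocusing the image by +2.00 D over the manifest distance correction in both eyes".

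**The glare conditions.** Before each one, Appendix K has both pupils measured without glasses, each while the other eye is exposed to the light. For photopic with glare: "To measure photopic with glare pupil size, have the subject (without glasses) look at a spot on the photopic with glare contrast sensitivity chart". For mesopic with glare: "Repeat the measurement on the second eye, and record the mesopic with glare pupil size for both eyes". This cannot be done with the second eye occluded, so the set-up has to be taken down. Appendix L does not say what replaces it, so the mode in these two conditions is unsettled. It cannot be called monocular.

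**How many scores come from the mesopic test without glare at 6 months.** The protocol gives two different lists of mesopic frequencies, so both are shown.

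| | Protocol 6.3 | Protocol 10.7 |
|---|---|---|
| Mesopic without glare | 3 | 4 |
| Mesopic with glare | 3 | 4 |
| Photopic with glare | 4 | 4 |
| All 6-month measures | 10 | 12 |
| Share directly affected | 3/10 = 30% | 4/12 = 33% |
| Scores per lens group | 3 × 65 = 195 | 4 × 65 = 260 |
| Scores in three groups | 585 | 780 |

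The shares refer to the 6-month visit. If the 1-month monocular measures are added to the denominator they become 3/20 = 15% and 4/24 = 17%.

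**The case against.** The strongest reply is that this is one carried-over sentence in a plan whose intention is otherwise clear. The heading, the preceding step, the opening of Appendix L, Appendix A and the SAP all point to binocular testing. Appendix E says on-screen prompts guide monocular or binocular set-up. Protocol 15.2 calls a training visit likely around the first 6-month visits. The planned analysis is descriptive with 90% confidence intervals (Protocol 20.3, SAP 7.4), and randomization lists are made per site (Protocol 10.4), so a site's practice should fall on all three lens groups. Nothing shows that any site would misread the text.

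Most of this stands, and it limits the weight of the point. It does not remove the contradiction. The sentence is a complete, operative instruction, the prompts and training do not correct it, and the training is only likely. The statement that sites may differ is a possibility, not a finding.

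Two cautions on the counts also stand. They measure exposure, not effect. SAP 7.4 also refers to averaging two log scores, so if each measure has two readings the counts are of analysed averages rather than recorded readings.

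**Conclusion.** The contradiction is real and should be corrected. As written, the 6-month mesopic test without glare is done with the first eye only, against the paragraph's own heading and every other statement of the test mode. The glare conditions have no stated eye set-up.

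The exposure is 30% to 33% of the 6-month contrast sensitivity measures, or 585 to 780 scores, assuming 65 evaluable subjects per group and one analysed score per frequency. The documents give no figure for the difference between one-eye and two-eye scores, so the size of any shift cannot be derived.

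The harm is mislabelled or mixed values in one condition of an additional safety endpoint. The primary endpoints are unaffected, and a biased comparison between lenses is not expected.

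**What to change.** 1. Reconcile the filter and occluder sentence in the 6-month paragraph with its heading. One possibility is a 1.5 ND filter before each eye in the trial frame, with no occluder, fitted before the filter on the M&S System is taken away. No section states a binocular filter arrangement, so the sponsor should confirm the wording.
2. Add a sentence saying that both eyes are tested open in all three lighting conditions at 6 months, including after the Appendix K pupil measurements.
3. Cover the point in the training that Protocol 15.2 already expects at or just before the first 6-month visits.

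Optionally, state that the trial-frame filters are for the mesopic conditions only.

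The cost is one corrected sentence, one new sentence and one training item. Neutral density trial lenses are already on the Appendix B equipment list, and no extra visits or staff are needed.
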